10.12	Conflict of Interest Policy	60
11	ABBREVIATIONS	60
12	REFERENCES	61

STATEMENT OF COMPLIANCE

The trial will be carried out in accordance with International Council for Harmonisation Good Clinical Practice (ICH GCP) and the following:

- United States (US) Code of Federal Regulations (CFR) applicable to clinical studies (45 CFR Part 46, 21 CFR Part 50, 21 CFR Part 56, 21 CFR Part 312, and/or 21 CFR Part 812)

National Institutes of Health (NIH)-funded investigators and clinical trial site staff who are responsible for the conduct, management, or oversight of NIH-funded clinical trials have completed Human Subjects Protection and ICH GCP Training.

The protocol, informed consent form(s), recruitment materials, and all participant materials will be submitted to the Institutional Review Board (IRB) for review and approval. Approval of both the protocol and the consent form must be obtained before any participant is enrolled. Any amendment to the protocol will require review and approval by the IRB before the changes are implemented to the study. In addition, all changes to the consent form will be IRB-approved; an IRB determination will be made regarding whether a new consent needs to be obtained from participants who provided consent, using a previously approved consent form.

1 PROTOCOL SUMMARY

1.1 Synopsis

- Title:** Phase 2 study of the PTH-independent Effects of Encaleret on Mineral Homeostasis in subjects with post-surgical hypoparathyroidism (PSH)
- Study Description:** This will be a single-site, proof-of-principle, open-label study to explore the PTH-independent effects of encaleret on calcium homeostasis in participants with low or undetectable PTH levels as a result of neck surgery (PSH).
- Objectives:** *Primary Objective:*
- Evaluate the PTH-independent effects of encaleret on renal calcium handling in participants with PSH.
- Secondary Objectives:*
- Evaluate the ability of encaleret to normalize blood calcium while maintaining a normal urinary calcium in participants with PSH.
- Tertiary/Exploratory Objectives:*
- Evaluate the ability of encaleret to increase serum iPTH levels in participants with PSH.
 - Evaluate the effect of encaleret on 1-alpha hydroxylase action by measuring 1,25-(OH)₂ Vitamin D levels.
 - Explore the dynamic effect of encaleret on blood and urinary calcium, iPTH, cAMP, 1,25-(OH)₂ Vitamin D, and urinary citrate.
 - Evaluate the effect of encaleret on bone turnover in participants with PSH.
 - Evaluate the effect of encaleret on phosphate, magnesium, and FGF23 levels.
 - Explore the effects of encaleret on 24-hour urine markers that impact stone formation
 - Examine the PK of encaleret in participants with PSH and explore PK-PD interactions.
 - Explore the effect of encaleret on bone and mineral homeostasis in the following sub-groups, *as defined in Section 9.3:*
 - Permanent hypoparathyroidism (Cohort 1)
 - Recent hypoparathyroidism (Cohort 2)
 - “PTH-Clamp” cohort
 - “Aparathyroid” cohort
 - Hyperthyroid cohort
 - Normothyroid cohort
 - Thyroid cancer cohort

2

Primary Endpoint:

- Percent change in Fractional Excretion of Calcium (FECa) from baseline (Day -1) to the final day of treatment (Day 6 or the last measurement while on encaleret). FECa calculated using fasting blood levels and spot urine collection.

Secondary Endpoints:

- Proportion of participants who achieve a concomitant normal or elevated fasting blood calcium (albumin-corrected calcium >8.5 mg/dL) and a normal 24-hour urinary calcium level (<250 mg/24 hours for women, <300 mg/24 hours for men) on encaleret at any point between day 1 and day 5.

Tertiary/Exploratory Endpoints:

- Percent change in Fractional Excretion of Calcium (FECa) from baseline (Screening visit) to the final day of treatment (Day 6 or the last measurement while on encaleret). FECa calculated using fasting blood levels and spot urine collection.
- Change in blood iPTH comparing average baseline iPTH to average peak iPTH on encaleret. The average baseline iPTH will include all baseline iPTH levels from the screening visit, Day -1, and pre-dose on Day 1. The average peak iPTH will average the peak iPTH levels on every day the patient is on encaleret (days 1 to 5). An increase in iPTH will be considered clinically significant if there is an increase both by 50% AND by more than 10 pg/dL.
- Change in 1,25-(OH)₂ Vitamin D on encaleret comparing the maximal level prior to receiving calcitriol (On Days 3-5) to baseline (Average of Day 1 Pre-dose levels). Increase will be considered significant if there is an increase of more than 50%. Participants who receive calcitriol prior to Day 3 will be excluded.
- Pharmacodynamic endpoints measured over 5 days of encaleret therapy:

- Blood iPTH – Absolute levels and change from baseline
- Albumin-corrected blood calcium – Absolute levels and change from baseline
- Ionized Calcium – Absolute levels and change from baseline
- Urinary calcium clearance (fractional excretion and 24-hour total excretion) – Absolute levels and change from baseline
- Serum levels of 1,25-(OH)₂ Vitamin D – Absolute levels and change from baseline
- Blood intact FGF23 (iFGF23) and C-terminal FGF23 (cFGF23) – Absolute levels and change from baseline
- Urine cAMP and citrate – Absolute levels and change from baseline
- Blood bone resorption marker, collagen cross-linked C-telopeptide (CTX) – Absolute levels and change from baseline
- Blood bone formation marker, blood procollagen type 1 N-propeptide (P1NP) – Absolute levels and change from baseline
- PK parameters such as maximum plasma concentration (C_{max}), time to maximum plasma concentration (t_{max}), apparent terminal half-life (t_{1/2}).
- Change in components of urine including: supersaturation, sodium, potassium, calcium, magnesium, chloride, phosphorus, sulfate, citrate excretion, oxalate, pH, uric acid, creatinine, osmolality, ammonium, urea nitrogen, protein catabolic rate

Study Population: Enrollment up to 30 male or female participants to achieve 15 to enter the treatment phase. Two cohorts:
Cohort 1: Permanent PSH (>1 year after surgery) with minimum of 7 and up to 10 participants
Cohort 2: Recent PSH (<1 year after surgery) with up to 5 participants

Phase: Phase 2

Description of Sites/Facilities National Institutes of Health (NIH) Clinical Center (CC)

Enrolling Participants:

Description of Study Intervention: Encaleret will be provided as an oral film-coated tablet. Each tablet contains 54 mg of encaleret as 60 mg of encaleret sulfate (CLTX-305). Participants will receive 3 tablets twice a day (BID).

Study Duration:	Estimated time from when the study opens to enrollment until completion of data analyses is approximately 12 months.
Participant Duration:	Total duration of study participation will be 101 to 277days for each subject including between 4 and180 days between the screening visit and initiation of therapy, and 90 day follow up after discontinuation of the study drug.

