1.3 Schedule of Activities (SOA)

Table A Schedule of Activities

	Screening	NIH CC Inpatient Treatment Visit							Discharge	FU Lab ⁷	Lab Phone FU ⁸	30- Day Phone FU ⁹	90-Day Phone FU ¹⁰
		Admission		BID Dosing									
Days	-180 to -2	-2 OR -1	-1	1	2	3	4	5	6	8-12	9-15	30 ± 7	90 ± 7
Informed Consent	X												
Admission to clinic/ inpatient floor ¹	X	X											
Demographi cs, Medical history	X												
Eligibility assessment	X												
Height	X												
Weight	X		X					X					
Vital signs ²	X		X	X	X	X	X	X	X				
Physical examination	X		X					X					
Aes and SAEs, Prior/ Concomitant meds	X	X	X	X	X	X	X	X	X	X	X	X	
NPO at midnight for morning fasting labs; water and medications ok			X	X	X	X	X	X	X				
Encaleret 162 mg q12h				X	X	X	X	X					
Calcium Carbonate, individualize d dosages			X	X	X	X	X	X					
Nutritionist Visit	X												
Quantify dietary calcium intake			X	X	X	X	X	X					

Stop magnesium and potassium citrate (last doses on day -3)		X	X										
Stop activated vitamin D and baseline calcium supplements (last doses on day -2) ³			X										
Start calcitriol if cCa < 8.5 mg/dL ³						X	X	X					
Discharge, resume conventional therapy									X				
Telephone Contact											X	X	X
Screening Lab Tests ⁴	X												
Safety laboratory testing ⁵										X			
Evening mineral panel (Ca, Mg, PO ₄ , albumin)			X										
Blood β-HCG pregnancy test (WOCBP only)	X		X							X			
Blood Sampling ⁶			X	X	X	X	X	X					
24-hour Urine (Ca, Mg, PO ₄ , Cr, Na, K, Citrate, pH)	X		X	X	X	X	X	X					
Timed interval urine collections ⁷				X	X	X	X	X					
Renal Ultrasound	X												
ECG, 12-lead	X		X	X	X	X	X	X					

Abbreviations: Adverse Event = AE; Albumin = Alb; Electrocardiogram = ECG; BID = Twice daily; Blood Pressure = BP; Calcium = Ca; Chloride = Cl; Concomitant Medication = Con. Meds; Creatinine = Cr; Early Termination = (ET); End of Treatment = EoT.

Follow-up = FU; Heart Rate = HR; Lactate Dehydrogenase = LDH; Intact Parathyroid Hormone = iPTH; Magnesium = Mg; NPO = Nothing by mouth; National Institute of Health Clinical Center = NIH CC; Parathyroid Hormone = PTH; Phosphate = PO₄; Phosphorus = P; Potassium = K; Prothrombin Time/ Prothrombin Time = PT/INR; Red Blood Cell Count = RBC; Thromboplastin Time = PTT; Serious Adverse Event = SAE; Women of Childbearing Potential = WOCBP

¹ Participants may complete the Screening Visit as outpatients or be housed overnight at NIH CC.

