Participants who complete the screening visit midweek have the option to stay overnight at NIH CC (or at local housing) during the intervening days prior to the start of Day -1. Participants also have the option of travel to be local to the NIH on day -2 and stay at NIH housing (e.g., The Edmond J. Safra Family Lodge) if available. Participants have the option of being admitted on Day -2 or Day -1.

² Vital signs include supine or sitting blood pressure (BP) by automated cuff, heart rate (HR), and respiratory rate, to be collected q8 hours during in-patient days.

³ Algorithm for calcium/calcitriol titration and encaleret stopping criteria found in Table D

⁴ Screening lab tests: CBC, Acute care panel, ionized calcium, eGFR, Liver Function Panel, mineral panel, iPTH, 25-OH Vitamin D, Lipid panel, CK, LDH, amylase, lipase, uric acid, Coagulation (PT/PTT/INR), urinalysis, HIV, Viral Hepatitis panel, FSH level test (postmenopausal women), spot urine: calcium, magnesium, phosphate, creatinine, and cAMP. TSH, Free T4

⁵ Safety lab tests: BMP, calcium, albumin, magnesium, phosphate, iPTH.

⁶ See Table B and C. Note attempts will be made to collect fasting calcium levels prior to the morning calcium dosage, however, calcium will be given to participants if clinically indicated (for example, in the setting of hypocalcemia).

⁷ Participants instructed to obtain outpatient laboratory testing, approximately 3-7 days after discharge from NIH CC.

⁸ Research team will contact the subject to review test results and provide guidance regarding clinical management as they transition to prior clinical care providers.

⁹ All participants will receive a FU call within 30 ± 7 days after last dose of the encaleret. If subject discontinues from the study early (ET), they will resume prior medication regimen, and study team will arrange FU labs within 3-7 days and FU calls at 30 ± 7 days and 90 ± 7 days after the last dose of encaleret as long as subject agrees.

¹⁰ Final close out phone call will assess for any unintended pregnancies in either the patient or a sexual partner.

Table B: Urine Assays

	Day 1-5 Timepoints relative to AM dose +/- 20 min. PM dose given at +12 hrs +/- 30 min, given after 12 hr timepoint lab draw
Daily Urine Assays	
Spot Urine Measurement Ca, Mg, PO4, Cr, cAMP	Day -1 (fasting) Day 1, Time 0
Osmolality, cAMP	Day 1, Time 0 Day 1-5: 16-24 hr
Timed Interval Urine Ca, Mg, PO4, Crvolume	Day 1-5: 0-4 hr, 4-12 hr, 12-16 hr, 16-24 hr

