24-Hour urine: Ca, Mg, PO4, Cr, Na, K, pH, Citrate Supersaturation Panel	Days -1 to 5 0-24 hrs (Start collection after first morning void and end 24 hours later) Day -1 and Day 5

Table C: Blood Sampling Days -1 to 5

Day -1: Baseline fasting labs including CBC, acute care panel, intact PTH, Ca, PO4, Mg, Cr, albumin, K, CK, Research blood, Bone turnover markers (CTX, P1NP), 25-(OH) Vitamin D, 1,25-(OH)₂ Vitamin D, cAMP, ionized calcium, TSH, FT4

		-30 min	-15 min	30 min	1 hour	2 hour	4 hour	12 hour	16 hour	24 hour
Day 1	Mineral labs	X	X	X	X	X	X	X	X	
	Safety Labs		X					X		
	Ionized Calcium		X				X	X	X	
	Research Blood	X	X			X	X	X	X	
	Bone Turnover Markers		X							
	1,25D	X	X							
	cAMP		X							
	Pk		X			X	X			
Day 2-4	Mineral labs		X	X			X	X	X	
	Safety Labs		X					X		
	Ionized Calcium		X				X	X	X	
	Research Blood		X				X	X	X	
	Bone Turnover Markers		X							
	1,25D		X							
	cAMP		X							
	Pk		X							
Day 5	Mineral labs		X	X	X	X	X	X	X	X
	Safety Labs		X					X		
	Ionized Calcium		X				X	X	X	X
	Research Blood		X			X	X	X	X	X
	Bone Turnover Markers		X							
	1,25D		X							X
	cAMP		X							X
	Pk		X			X	X			

Mineral Labs: Intact PTH, Ca, PO4, Mg, Cr, Albumin

Safety Labs: Acute care panel (Na, K, Cl, CO₂, BUN, Cr, eGFR), CK

Research Blood

Bone turnover Markers: CTX, P1NP

1,25-(OH)₂ Vitamin D, cAMP

a

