
Explore the dynamic effect of encaleret on blood and urinary calcium and citrate, iPTH, cAMP, and 1,25-(OH)₂ Vitamin D.
 
Evaluate the effect of encaleret on bone turnover in participants with PSH.
 
Evaluate the effect of encaleret on phosphate, magnesium, and FGF23 levels.
	
Percent change in Fractional Excretion of Calcium (FECa) from baseline (Screening visit) to the final day of treatment (Day 6 or the last measurement while on encaleret). FECa calculated using fasting blood levels and spot urine collection.
 
Pharmacodynamic endpoints measured over time over 5 days of encaleret therapy:
 
 • Blood iPTH – Absolute levels and change from baseline • Albumin-corrected blood calcium - Absolute levels and change from baseline in cCa • Ionized Calcium – Absolute levels and change from baseline • Urinary calcium clearance (fractional excretion and 24- 	These endpoints will allow us to further explore the effect of encaleret on other markers of bone and mineral metabolism and identify areas for future study.

OBJECTIVES	ENDPOINTS	JUSTIFICATION FOR ENDPOINTS

Explore the effects of encaleret on 24-hour urine markers that impact stone formation
	
hour total excretion) - Absolute levels and change from baseline
 
 • Serum levels of 1,25-(OH)₂ Vitamin D - Absolute levels and change from baseline • Blood iFGF23 and cFGF23 - Absolute levels and change from baseline • Urine cAMP and citrate - Absolute levels and change from baseline • Bone resorption markers collagen cross-linked C-telopeptide (CTX) - Absolute levels and change from baseline • Bone formation markers – blood procollagen type 1 N-propeptide (P1NP) - Absolute levels and change from baseline • Change in components of urine including: supersaturation, sodium, potassium, calcium, magnesium, chloride, phosphorus, sulfate, citrate excretion, oxalate, pH, uric acid, creatinine, osmolality, ammonium, urea nitrogen, protein catabolic rate 	

 • Examine the PK of encaleret in participants with PSH and explore PK-PD interactions. 	
 • PK parameters such as maximum plasma concentration (C_{max}), time to maximum plasma concentration (t_{max}), apparent terminal half-life (t_{1/2}) 	

OBJECTIVES	ENDPOINTS	JUSTIFICATION FOR ENDPOINTS

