5.5 Lifestyle Considerations

During this study, participants are asked to:

- Consume approximately 1000 mg of daily calcium from their diet, with assistance from a nutritionist.
- Refrain from donating blood at least 12 weeks prior to the admission visit to one year after the last dose of the drug.

- Refrain from eating food from midnight until the next morning during the admission visit

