8.2 Study Evaluation & Procedures

The following procedures and imaging assessments will occur according to Section 1.3 Schedule of Activities.

All participants must sign the informed Consent Form (ICF) prior to any study-related procedures. Screening must be completed within 180 days prior to admission to the NIH CC (See [Table A](#) for Schedule of Activities).

Screening Visit: The first screening visit will be conducted at the NIH CC to determine subject eligibility, document current metabolic status, and assess dietary calcium intake. Participants may complete the screening assessments as outpatients or be housed overnight at NIH CC. Participants who complete the screening visit midweek have the option to stay overnight at NIH CC during the intervening days prior to Day -1. Each subject's current treatment regimen will be assessed by NIH investigators in relation to presence/absence and control of hypocalcemia-related complaints and symptoms, and assessment of blood and urine analytes including blood and urine calcium and phosphate. NIH investigators may recommend adjustments to a subject's outpatient regimen during the screening period, in accordance with the accepted goals of achieving cCa in the low normal range, while minimizing hypercalciuria. Unscheduled outpatient laboratory assessments, if required, will be arranged through outpatient laboratories with results transmitted to and reviewed by the investigators as standard of care. Participants who complete the screening process and meet inclusion/exclusion criteria, may be scheduled for admission for the treatment period of the protocol.

Procedures/evaluations planned as part of the screening visit include:

- History and Physical examination
- Height and Weight
- Vital Signs
- Nutritionist Assessment
- Blood laboratory assessment
- Electrocardiogram (ECG)
- 24-hour urine collection (may be performed after the visit if more convenient for the patient)

- Renal Ultrasound

After completing screening assessments, any AE/SAE reported by a subject, whether or not study drug has been administered, will be recorded by the investigators. Any AE/SAE prior to dosing will be categorized as “Baseline” and any AE/SAE after dosing will be categorized as “treatment-emergent.”

Treatment Period:

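### The exploratory FECa endpoint needs a fasting Screening sample, but the schedule does not ask for fasting at Screening (minor)

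*Combined protocol and SAP*

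**What the plan says.** The Synopsis (Section 1.1) and Section 3 list an exploratory endpoint defined as "Percent change in Fractional Excretion of Calcium (FECa) from baseline (Screening visit) to the final day of treatment". Both add the sampling condition, in Section 3 as "FECa calculated using fasting blood levels and spot urine collection". Neither makes an exception for the Screening baseline.

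Four places bear on whether the Screening sample is fasting:

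- **Table A, fasting row (Section 1.3).** The row "NPO at midnight for morning fasting labs; water and medications ok" is marked for Day -1 and Days 1 to 6. The Screening column is blank.
- **Section 5.5.** The instruction to participants is "Refrain from eating food from midnight until the next morning during the admission visit". It does not mention the screening visit.
- **Table A, footnote 4.** The Screening tests include "spot urine: calcium, magnesium, phosphate, creatinine, and cAMP" along with the blood tests, with no fasting or time-of-day condition.
- **Section 8.2.** "Participants may complete the screening assessments as outpatients or be housed overnight at NIH CC", so an overnight stay under supervision is optional.

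The Day -1 sample is treated differently. Table C begins "Day -1: Baseline fasting labs including CBC", and Table B marks the Day -1 spot urine as fasting.

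**The concern.** The endpoint definition and the schedule disagree. The definition needs a fasting blood and urine pair at Screening, and nothing in the schedule obliges anyone to produce one. Nor do the documents say what to do with a Screening sample that turns out not to be fasting.

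If such a sample is used, the percent change compares two sampling states as well as two treatment states. A difference due to food or a recent calcium tablet would be read as part of the encaleret effect. What is at stake is the interpretation of one exploratory endpoint. A missed fast at Screening cannot be repaired later, so the gap is worth closing while participants are still being screened.

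**Working it through.** **1. Definition against schedule**

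| Item | Screening | Day -1 | Day 6 |
|---|---|---|---|
| Role in this endpoint | baseline | none (baseline of the primary endpoint) | final value |
| Table A fasting row | blank | marked | marked |
| Section 5.5 overnight fast | not covered | covered (admission) | covered (admission) |
| Blood | footnote 4, no fasting stated | Table C, fasting | Table C, Day 5 24-hour draw |
| Spot urine | footnote 4, no fasting stated | Table B, fasting | not listed in Table B |

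The definition asks for fasting at Screening and no scheduling text supplies it. Footnote 6 of Table A aims to draw fasting calcium before the morning calcium dose. It is attached to the blood-sampling row, which runs from Day -1 to Day 5, so it does not cover Screening either.

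The last row shows a second gap. Table B lists spot urine on Day -1 and at Day 1 Time 0 only. The latest urine it lists is the Day 5 collection (the 16-24 hour interval and the 24-hour total), yet the endpoint names a Day 6 value from a spot urine.

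**2. The plan's own figures, as a yardstick**

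The plan gives no precision figure for this endpoint. Section 9.2 gives detectable changes for the primary endpoint: two-sided 0.05 paired t-test, SD 20%, 80% power. Solving the noncentral t power equation with n - 1 degrees of freedom gives:

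- n = 15: 15.56% (stated 16%)
- n = 10: 19.92% (stated 20%)
- n = 5: 33.64% (stated 34%)

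The stated figures reproduce.

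**3. What a mismatched baseline would do**

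Let the Screening FECa be (1 + x) times the same participant's fasting value, with no drug effect. The recorded change is then 1/(1 + x) - 1. The documents give no fed or fasting FECa, so every x below is an assumption.

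- x = +25%: 1/1.25 - 1 = -20%
- x = +50%: 1/1.50 - 1 = -33%
- x = -10% (for example, a thiazide lowering urinary calcium at Screening): 1/0.90 - 1 = +11%

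Conversely, the offset that alone produces a fall of 16% is 1/(1 - 0.16) - 1 = 19%. An offset of that order would equal the change that Section 9.2 regards as detectable with 15 participants. This is only a scale for comparison, because the plan names no specific test for this endpoint.

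**The case against.** The strongest reply is that the definition already requires fasting, so a non-fasting Screening value does not qualify. The schedule's silence is not evidence that anyone was fed. Participants may stay overnight, and samples are handled under a Laboratory Manual (Section 8.2.3) that is not among the documents and may contain a fasting instruction. The endpoint is one of many exploratory ones, and its baseline may lie up to 180 days before admission on a different regimen, which makes the comparison descriptive in any case. All of this stands and sets the severity. It does not remove the disagreement between definition and schedule.

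A reader might infer more than the documents support:

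- **That a spurious fall is to be expected.** Neither the offset nor its direction is given. Section 2.1 links conventional therapy to high urinary calcium, but no passage quantifies the effect of a meal on FECa. Inclusion criterion 7 allows thiazides to be in use at Screening, which could act the other way.
- **That the artefact would reach the plan's threshold for success.** The fall of more than 40% in Section 6.1.2 belongs to the primary endpoint and to early drug discontinuation. The 50% offset does not reach it (-33%).
- **That there is no fasting sample close to usual therapy.** Day -1 is fasting and comes one day after the last home calcium and calcitriol doses, although citrate, magnesium and thiazides may already have been stopped.
- **That this is the trial's only FECa comparison with conventional therapy.** The protocol does not give the endpoint that purpose; Section 3 groups it with the dynamic-effect endpoints.

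**Conclusion.** The point holds as a minor inconsistency. The endpoint requires a fasting Screening baseline, and the schedule as written allows a non-fasting one. If that happens, a sampling-state difference of unknown size enters the percent change. The figures of -20% and -33% rest on assumed offsets of 25% and 50% and on no drug effect. They show how the error would pass through, and are not estimates of it.

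The Screening gap does not touch the primary endpoint, whose baseline is the fasting Day -1 sample. Requiring a fast at Screening would not make the comparison fully like-for-like either: the interval before treatment and the change of regimen would remain, and the final spot urine is itself not scheduled in Table B.

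**What to change.** - Mark the fasting row of Table A for Screening and extend the Section 5.5 instruction to that visit.
- Collect the Screening blood and spot urine in the morning, fasting. Apply footnote 6's existing wording on drawing before the morning calcium dose, including its clinical exception. The mark in Table A is not enough by itself, because that row permits medications.
- Record fasting status for participants already screened. Leave non-fasting Screening values out of this endpoint, or report them separately as descriptive, and state the rule before the FECa results are examined.
- Reconcile the final value: either add a Day 6 fasting spot urine to Table B or say which listed urine collection is used. The primary endpoint names the same Day 6 value, so this clarification serves both.

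The cost is small. The Screening visit and its samples are unchanged, but some participants will need a morning slot. Some existing Screening values may drop out; Section 2.3.1 reports six participants already exposed, of up to 15 to be treated, so the loss could be a noticeable share of this exploratory endpoint.
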